(S)AE	(Serious) Adverse Event
SPC	Summary of Product Characteristics (in Dutch: officiële productinformatie IB1-tekst)
Sponsor	The sponsor is the party that commissions the organisation or performance of the research, for example a pharmaceutical company, academic hospital, scientific organisation or investigator. A party that provides funding for a study but does not commission it is not regarded as the sponsor, but referred to as a subsidising party.
SUSAR	Suspected Unexpected Serious Adverse Reaction
Wbp	Personal Data Protection Act (in Dutch: Wet Bescherming Persoonsgegevens)
WMO	Medical Research Involving Human Subjects Act (in Dutch: Wet Medisch-wetenschappelijk Onderzoek met Mensen)

SUMMARY

Rationale: Cancer patients receiving treatment such as chemotherapy experience a variety of symptoms that interfere with their appetite and their ability to eat and enjoy meals. Several studies suggest that nutritional intake increases when the patient is satisfied about the quality of the meals. Therefore, adapting meals in a way that responds to these symptoms might be a good strategy to improve patient satisfaction, nutritional status and hence, quality of life. In this vein, we hypothesize that meals from FoodforCare at Home will contribute to the quality of life of advanced abdominal cancer patients undergoing chemotherapy when compared to usual care. Also, we expect that this strategy will have a positive effect on patient satisfaction, other nutrition-related issues, including nausea and vomiting, on nutritional intake per se and hence, on the nutritional status. Additional benefits might include reduced use of medication, especially anti-emetics.

Objective: To study whether FoodforCare at Home is superior to usual care with respect to quality of life in advanced abdominal cancer patients undergoing chemotherapy.

Study design: Randomized controlled trial

Study population: Advanced abdominal cancer patients undergoing chemotherapy, 18 years and older.

Intervention and procedure: Inclusion will take place at the department of Medical Oncology at the start of palliative chemotherapy. Patients will be randomly assigned to one of two groups before the start of the second cycle of chemotherapy. The intervention group will receive meals from FoodforCare at Home and the control group will continue their regular diet for 3 weeks between the 2nd and 3rd cycle of chemotherapy. The FoodforCare at Home meals will be delivered at the patient's home by research assistants or AYA's. These are Adolescents and Young Adults with cancer who are also trained to perform the measurements.

Main study parameters/endpoints: The main study parameter is quality of life of patients receiving FoodforCare at Home compared with patients receiving their usual diet. This will be evaluated by the EORTC-QLQ-c30 at all time points. The secondary endpoints are patient satisfaction, nutritional status, nutritional intake, performance scale, medication use, symptoms and quality of life of the partner/caregiver.

Nature and extent of the burden and risks associated with participation, benefit and group relatedness: There are no additional tests or hospital tests necessary for the patient. This study will not confer any no additional risks. Food will be delivered within the expiration dates and the meals will be prepared according to the regular hygienic and food safety criteria that are valid. Possible serious reactions to the meals will be noted as SAE's.

1. INTRODUCTION AND RATIONALE

Cancer patients receiving treatment such as chemotherapy often experience a variety of symptoms that interfere with their ability to eat and enjoy meals. These symptoms like loss of appetite, nausea and pain are referred to as nutrition impact symptoms [1]. Patients with several of these symptoms are more likely to experience a decline in nutritional intake [2]. Thus, reducing symptoms might lead to an improved nutritional intake. Furthermore, several studies suggest that nutritional intake increases when the patient is satisfied about the quality of the meals [3]. Therefore, adapting meals in a way that responds to these symptoms might be a good strategy to improve patient satisfaction and nutritional status.

Abdominal malignancies constitute a considerable proportion of all cancer types. Worldwide, the incidence of this type of tumors is 7.2 million and in the Netherlands alone this comprised more than 30.000 cases in 2015 [4]. Colon cancer is the most prevalent type of cancer within this group with an incidence of more than 15.500 in 2015 [5]. Furthermore, not unexpected, patients with abdominal cancer most frequently seem to experience symptoms that can interfere with eating [6]. For example, patients with gynecological tumors indicate to have some form of gastro-intestinal complaints in 70% of cases during hospitalization with loss of appetite, nausea and reduced taste being the most prominent features [7]. Gastro-intestinal side effects in colorectal cancer concern primarily abdominal fullness, nausea and vomiting [6, 8]. Besides, taste and smell alterations are well-known side effects of chemotherapy [9]. In the palliative stage, 70% of the patients experiences four or more diet-related symptoms [10]. It is important that special attention goes to symptom management in this stage because of the association between symptoms and quality of life [11, 12]. Accordingly, the main focus of palliative care is alleviating symptoms and increasing quality of life [10].

As a result of the symptoms caused by the disease and the treatment, palliative patients have a high risk for the development of malnutrition. This is due to decreased nutritional intake and disease-related metabolic changes resulting in a disturbed carbohydrate, fat and protein metabolism [10]. These metabolic disturbances are further exaggerated by the loss of appetite that is a common symptom in palliative patients [13, 14]. This interaction is called the anorexia-cachexia syndrome and can lead to cachexia [10]. Prevalence of cachexia varies between cancer types but the gastrointestinal tract has one of the highest rates with over half of all patients being affected [15]. In addition, cachexia is associated with reduced survival and decreased quality of life [16]. Therefore, maintaining and improving nutritional status is important during palliative treatment in order to improve quality of life. However, maintaining or improving nutritional status is only possible depending on the state of the disease [10].

Several studies show that patients often receive too little nutritional care which causes symptoms to worsen and frequently leads to hospitalization [17, 18]. Proper nutritional care and food provision contribute beneficially to maintaining nutritional status and quality of life of patients [3, 18]. Next to the fact that the meals should meet the nutritional requirements of the patients, other factors such as food quality and patients' satisfaction are important as well. In general, hospital food has a negative connotation due to the unfavorable contrast with homemade food [3, 19]. Patients value food quality and service quality the most and therefore, these are important predictors for patient satisfaction and quality of life [19, 20].

Furthermore, there is evidence of a positive association between patient satisfaction and energy intake [20].

There are various types of meal services that are used in the hospital setting and in the past years these have been optimized to the preferences and needs of hospitalized patients [21-24]. However, research has mainly focused on foodservice satisfaction in hospitals while this phenomenon might also be relevant for palliative patients at home, also in terms of time management. Studies on home delivered meal services mostly have been carried out in elderly people. In this population, improvements were seen in nutritional and functional status although most studies were cross-sectional with small sample sizes [25]. Few studies focused on patient satisfaction and quality of life [26, 27]. Frongillo et al. reported an overall satisfaction of 77% of the elderly who received home-delivered meals [26].

In the Netherlands, an innovative hospital food formula, FoodforCare, was recently developed and implemented hospital-wide in the academic hospital (Radboudumc) in Nijmegen. This formula consists of dishes with high nutritional values that aim at improving appetite and contributing to patients' wellbeing. FoodforCare makes use of small, frequent meals in order to reduce the risk of gastro-intestinal complaints and to reduce plate waste. There are studies stating that smaller portions are related to reductions in plate waste and an increase in energy intake [28-30]. In a recent pilot, so-called onco-proof products were offered to cancer patients. These products take account of the special consequences of the presence and treatment of the underlying condition for taste and smell and are rich in energy and protein. Patients who were submitted to this service described that they experienced lower levels of nausea when using these products compared to usual hospital meals. A tentative conclusion was formulated that this concept has a positive effect on the wellbeing and status of the patients.

It takes robust and well-designed studies to assess determine whether any meal service at home positively contributes to symptom management and quality of life in advanced abdominal cancer patients. The hypothesis of the present study is that FoodforCare at Home will be superior to usual care with respect to quality of life of advanced abdominal cancer patients undergoing chemotherapy. Furthermore, we expect that this meal service will have a beneficial effect on symptoms, patient satisfaction, performance scale, on nutritional intake and therefore, on the nutritional status of the patients. Another positive effect might result from a reduction in medication use (e.g. anti-emetics) and an improved quality of life of the partner/caregiver.

2. OBJECTIVES

Primary objective:

To study whether FoodforCare at Home is superior to usual care with respect to quality of life in advanced abdominal cancer patients undergoing chemotherapy.

Secondary objectives:

1. To reduce diet-related symptoms in these patients by using FoodforCare at Home compared to usual care.
2. To improve nutritional intake (adequate protein and energy intake) in these patients by using FoodforCare at Home compared to usual care.
3. To improve the nutritional status of these patients by using FoodforCare at Home compared to usual care.
4. To improve the functional status of these patients by using FoodforCare at Home compared to usual care.
5. To reduce medication use for the purpose of treating diet-related symptoms in these patients by using FoodforCare at Home compared to usual care.
6. To improve quality of life of the partners/caregivers of these patients by using FoodforCare at Home compared to usual care.
7. To improve patient satisfaction towards nutrition in these patients by using FoodforCare at Home compared to usual care.

3. STUDY DESIGN

A randomized controlled trial will be performed in palliative abdominal oncology patients at home. Inclusion will take place at the department of Medical Oncology at the start of palliative chemotherapy. The study is intended to be performed from March 2017 to July 2018. Patients will be randomly assigned to one of two groups before the start of the second cycle of chemotherapy because it is expected that FoodforCare at Home will make the largest difference during this cycle. The intervention group will receive meals from FoodforCare at Home and the control group will continue their regular diet for three weeks from the second cycle of chemotherapy until the next cycle of chemotherapy. Before the start of this study, a pilot study will be performed to determine whether the intervention is feasible in terms of logistics and delivery of the meals for example.

Measurements will take place at four time points during the study period i.e. before the start of chemotherapy, at the 2nd cycle of chemotherapy, at the 3rd cycle of chemotherapy and three month after T3 (figure 1). These measurements will be performed by AYA's/research assistants who will visit the patients at home. Time point 1, before the start of chemotherapy, will serve as the baseline measurement. At this moment, informed consent will be obtained and signed by the patient and the MUST score will be determined. Quality of life of patient and caregiver, nutritional intake, nutritional status, functional status and medication use will be assessed at all time points. For quality of life, the EORTC-QoL-C30 questionnaire will be filled in by the patients and the Caregiver Reaction Assessment by their caregivers. Nutritional status will be assessed using the handgrip strength measurement, the PG-SGA and performance scale by means of the Karnofsky score and the SPPB. Data on nutritional intake will be recorded using a 3-day food diary, which the patients will fill in by themselves. Medication use will be obtained from the patient's medical file. Additionally, during the intervention period, patients will record their symptoms using 'Utrecht Symptoom Dagboek' and medication use will be assessed by using a diary. At time point 3, patient satisfaction in the intervention group will be assessed by the Net Promoter Score with additional questions. An overview of the measurements can be found in table 1.

Figure 1. Flowchart of the study design of the FoodforCare at Home study.

[figure not shown]

Table 1. Measurements performed at each time point during the FoodforCare at Home study

	Before chemotherapy	2nd cycle chemotherapy	3rd cycle chemotherapy	3 months after T3
Informed consent	X			
MUST score	X			
QoL patient	X	X	X	X
QoL caregiver	X	X	X	X
Nutritional intake	X	X	X	X
PG-SGA	X	X	X	X
Handgrip strength	X	X	X	X
Performance scale	X	X	X	X
Medication use	X	X	X	X
Patient satisfaction			X	

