4.2 Inclusion criteria

In order to be eligible to participate in the study, the patient must meet all of the following criteria:

- age 18 years or older
- diagnosed with advanced colon or gynecological cancer
- receiving primary or secondary palliative chemotherapy according to a three weekly schedule
- living within a 40 km radius around the Radboud University Nijmegen Medical Centre
- written informed consent

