4.4 Sample size calculation

The sample size calculation is based on the primary outcome of this study: the EORTC-QoL-C30 questionnaire for quality of life. The primary outcome of this study is the difference in quality of life between the 2 groups at the start of the 3rd cycle of chemotherapy. Based on literature, advanced cancer patients with gynecological tumors and tumors of the colon have a mean score of approximately 60 points with a standard deviation of 22 points on the EORTC-QoL-C30 questionnaire. Assuming a difference of 10 points, on a scale of 0-100 points, is a clinically relevant difference in favor of FoodforCare at Home, we estimate that 76 patients are needed in each group in order to obtain a power of 80% (two-tailed t-test, alpha=0.05). Assuming a drop-out rate of 20%, this means a total of 180 patients. In order to improve the power significantly, we will make use of the ANCOVA test [31]. By multiplying the number of patients with $(1-(\rho^2))$ a total of 164 patients will be needed. The correlation between the baseline and follow-up outcome T2 (ρ) is estimated at 0.3.

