6.6 Follow-up of subjects withdrawn from treatment

When patients withdraw from the study after time point 3, these data may (if authorized by the patient) be used for analyses.

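### The primary time point T3 is the start of cycle 3, an event after randomisation, with no window and no rule for patients whose cycle 3 is late or never given

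*Combined protocol and SAP*

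**What the plan says.** Section 4.4 defines the primary outcome as "the difference in quality of life between the 2 groups at the start of the 3rd cycle of chemotherapy". Section 3 places the measurements after baseline "at the 2nd cycle of chemotherapy, at the 3rd cycle of chemotherapy and three month after T3", and Table 1 has the same columns. T3 is therefore set by a chemotherapy event, and T4 is counted from T3.

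The meal period is described in more than one way. Section 3 has it run "for three weeks from the second cycle of chemotherapy until the next cycle of chemotherapy". The Summary says "for 3 weeks between the 2nd and 3rd cycle of chemotherapy". Section 5.1 gives three weeks with no reference to a cycle, and Section 6.1.2 sets the symptom diary at three weeks. Section 9.5 places the last measurement three months after the intervention period, whereas Section 3 counts it from T3.

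Eligibility (Section 4.2) requires patients to be "receiving primary or secondary palliative chemotherapy according to a three weekly schedule". On where measurements are made, Section 3 says: "These measurements will be performed by AYA's/research assistants who will visit the patients at home".

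The readable text gives no visit window and no rule for a delayed or cancelled cycle 3. Section 6.6 covers only one case: "When patients withdraw from the study after time point 3, these data may (if authorized by the patient) be used for analyses". Section 8.1 specifies intention to treat. Section 8.2 specifies a repeated-measures mixed model with full maximum likelihood, and does not say whether time enters as nominal visit or actual days.

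**The concern.** A time point fixed by the calendar exists for every randomised patient. One fixed by the next infusion exists only for patients who receive that infusion, and it moves with the date of the infusion. Both happen after randomisation.

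In palliative chemotherapy, stopping or postponing a cycle plausibly reflects how the patient is doing. The documents do not say so and give no rates, so this is an inference. It is a reasonable one: Section 6.1.3 has toxicity monitored throughout, and Section 6.4.1 allows withdrawal for urgent medical reasons. The meals are expected to affect symptoms, intake, nutritional status and performance (Sections 1 and 2), so whether and when T3 occurs could differ between the arms.

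At stake is the comparability of the arms at the single time point on which the sample size rests. Patients who could still be measured at home may have no primary value, and those with a delay may be measured at a different distance from their last infusion and from their last meal.

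**Working it through.** **Inputs from the documents.** Section 4.4: difference 10, SD 22, two-sided alpha 0.05, power 80%, ρ = 0.3, drop-out 20%, total 164. Section 4.2: three-weekly cycles. Sections 3 and 4.4: T3 at the start of cycle 3, T4 three months later. The documents give no rate of stopping or delay, no difference between arms in either, and no score gap; those values are assumed below.

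**1. The plan's own figures.** Per group, 2 × (1.96 + 0.84)² × 22² / 10² ≈ 76, as stated. Taking the plan's 180 as given, 180 × (1 − 0.3²) = 180 × 0.91 = 163.8, i.e. 164, as stated. The timing of T3 does not enter either figure.

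**2. What the definition gives in each case, read literally.**

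| Cycle 3 | T3, from start of cycle 2 | T3, from end of three weeks of meals | T4 |
|---|---|---|---|
| On time | 3 weeks | 0 | T3 + 3 months |
| Late by d weeks | 3 + d weeks | d weeks after, if meals stop at three weeks; 0, if meals run until cycle 3 | T3 + 3 months, so also d weeks late |
| Never given | not defined | not defined | not defined |

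The two descriptions of the meal period agree only in the first row. The three-weekly requirement is an entry criterion and does not keep a patient in that row.

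**3. What the planned model recovers.** Under maximum likelihood, a patient without T3 still contributes T1 and T2. Missingness that depends only on those observed values is handled. A decline between T2 and the planned cycle 3 that leads to stopping is not visible in the primary outcome before T3, so missingness that depends on it is not handled. If time enters as nominal visit, delay is ignored.

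**4. Size, as a completers-only illustration.** Suppose patients without T3 would have scored g points below the others, with the same g in both arms. An arm with missing share p then has a completers' mean p × g above its mean over all randomised patients. The shift in the difference (intervention minus control) is (p_I − p_C) × g.

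| Assumed missing, intervention vs control | g = 10 | g = 20 |
|---|---|---|
| 10% vs 15% | −0.5 | −1.0 |
| 15% vs 25% | −1.0 | −2.0 |
| 10% vs 30% | −2.0 | −4.0 |
| 20% vs 20% | 0 | 0 |
| 25% vs 15% | +1.0 | +2.0 |

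For scale, with 164 × 0.8 ≈ 131 evaluable, the standard error of the adjusted difference is 22 × √0.91 × √(4/131) ≈ 3.67. The first row is therefore 0.5/3.67 to 1.0/3.67, or 0.14 to 0.27 standard errors. This formula describes a comparison of completers, not the planned mixed model.

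**The case against.** The strongest reply is that the plan can be read as fixing a three-week period. Section 5.1 and the symptom diary in Section 6.1.2 say three weeks, Section 9.5 counts the last measurement from the end of the intervention, and entry requires three-weekly chemotherapy. On that reading, the reference to the next cycle only describes the expected schedule. Visits are at home, nowhere is it said that a patient who stops chemotherapy is withdrawn or left unmeasured, and Figure 1, which is not shown in the text, may add timing detail. This establishes ambiguity. It does not override Section 4.4, which ties the primary outcome to the start of cycle 3.

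Four stronger inferences are tempting and are not supported:

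- **That the plan drops patients who stop chemotherapy.** It is silent. They lack a defined T3; no rule says to skip them.
- **That the primary analysis is biased by a known amount.** The planned analysis is intention to treat with a maximum-likelihood mixed model, which uses T1 and T2 from patients without T3. The figures above are for completers only, and with equal rates and gaps the shift is zero.
- **That power is lost beyond the plan's allowance.** Nothing in Section 4.4 shows that the 20% drop-out excludes patients who never start cycle 3. Adding them on top could count them twice.
- **That the meals act on progression.** The stated expectations concern symptoms, intake, nutritional and functional status, medication use, satisfaction and quality of life. Progression is not among them.

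**Conclusion.** The point stands as a weakness in the definition of the primary time point, worth correcting before the trial starts. As written, T3 and T4 are undefined for a patient whose chemotherapy stops after cycle 2. With a delay they move, and T3 may then fall after three weeks of meals have ended. That this is informative rests on the inference that stopping and delay follow the patient's condition. The mixed model gives partial protection, short of decline arising after T2.

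Neither the direction nor the size of any bias can be determined from the documents. On the milder assumed values (10% versus 15% missing, gap 10 to 20 points), a completers-only comparison would shift by 0.5 to 1.0 point against the intervention, which is small beside the 10-point target. Larger assumed differences between the arms give more, and reversed ones change the sign. None of the plan's stated sample size figures is shown wrong by this point. The case for change rests mainly on a better rule being available at little cost.

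**What to change.** - Define T3 at the plan's own three weeks after the start of cycle 2, with a short stated window that closes before any cycle 3 infusion. A window extending past three weeks would let on-time patients be measured after that infusion while delayed patients had received none.
- Measure T3 at home, in both arms, in every randomised patient who still consents, whether or not cycle 3 starts on time or at all.
- Count T4 from the same anchor, and record the actual date of cycle 3, or that it was not given.
- Align Sections 3, 4.4 and 6.6 and Table 1 with this definition. State in Section 8.2 how time enters the model and how values missing through death or refusal are handled, since a calendar date does not supply those.
- The sponsor must reconcile the two descriptions of the meal period (Summary and Sections 3, 5.1 and 6.1.2).

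The cost is protocol wording. Measurements are already home visits, so there are no extra visits, and the sample size does not change. The small downside is that some T3 visits will no longer coincide with cycle 3; recording its date allows this to be examined.

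### The named baseline (T1) lies a full chemotherapy cycle before the meals, the QLQ-C30 already collected at cycle 2 (T2) has no baseline role, and the correlation of 0.3 is labelled T2 although the primary outcome is at T3

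*Combined protocol and SAP*

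**What the plan says.** **Time points.** Section 3 lists four measurements: "before the start of chemotherapy, at the 2nd cycle of chemotherapy, at the 3rd cycle of chemotherapy and three month after T3". In the protocol's own numbering these are T1 to T4. Of the first it says: "Time point 1, before the start of chemotherapy, will serve as the baseline measurement". Table 1 shows patient quality of life at all four.

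**Randomisation and meals.** "Patients will be randomly assigned to one of two groups before the start of the second cycle of chemotherapy" (section 3). The meals run from cycle 2 to cycle 3. Eligible patients are "receiving primary or secondary palliative chemotherapy according to a three weekly schedule" (section 4.2), so T1 precedes the meals by about three weeks of treatment.

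**Primary outcome.** Section 4.4 defines it as the "difference in quality of life between the 2 groups at the start of the 3rd cycle of chemotherapy", which is T3.

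**Correlation.** Section 4.4 plans an ANCOVA, reduces the sample by the factor 1 − ρ², and adds: "The correlation between the baseline and follow-up outcome T2 (ρ) is estimated at 0.3".

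**Analysis.** Section 8.2 specifies a repeated-measures mixed model for the course of quality of life and the group difference. It names no baseline quality-of-life covariate and adjusts for confounders only where baseline is imbalanced.

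**Order of steps.** The readable text does not say whether the T2 questionnaire comes before or after the patient learns the allocation. Patients are not blinded (section 6.3), and the individual intake with the meal provider falls between allocation and the first meals (section 6.2).

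**The concern.** The sample size takes credit for a baseline adjustment that the analysis section does not commit to. The baseline it points to is also not the measurement closest to the start of the intervention. T1 is taken before any chemotherapy. T2 is taken after one cycle, so it can reflect how the patient tolerated treatment, and it lies one cycle from the primary outcome instead of two. It is therefore plausible, though the documents give no figure, that T2 predicts T3 better than T1 does.

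Separately, ANCOVA at T3 needs the correlation of the covariate with T3. Read literally, section 4.4 gives the correlation of T1 with T2, and neither of those is the primary outcome. The whole step from 180 to 164 rests on that one number.

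At stake are the precision of the primary comparison and whether the planned number can be justified on paper. T1 is measured before randomisation, so adjusting for it is unbiased.

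**Working it through.** **Inputs from section 4.4.** Patients "have a mean score of approximately 60 points with a standard deviation of 22 points on the EORTC-QoL-C30 questionnaire". The target difference is 10 points, two-sided alpha 0.05, power 80%, 76 per group, dropout 20%, total 180, ρ = 0.3, final total 164.

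**Step 1: reproduce the plan's figures.**
- Per group, normal approximation: 2 × (1.960 + 0.842)² × 22² / 10² = 75.98, so 76. An exact t-test gives 79.5% power at 76.
- Dropout: 152 × 1.2 = 182.4, close to the stated 180.
- ANCOVA factor: 180 × (1 − 0.3²) = 180 × 0.91 = 163.8, so 164.

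**Step 2: evaluable patients.** 164 × 0.8 = 131.2, or 65.6 per group.

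**Step 3: power at T3 for a covariate with correlation ρ to T3.** The residual SD is 22 × √(1 − ρ²). The standard error is that SD × √(2/65.6). Power is from the noncentral t distribution.

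| ρ (covariate with T3) | 1 − ρ² | Residual SD | SE of difference | Power |
|---|---|---|---|---|
| 0 | 1.00 | 22.0 | 3.84 | 73.4% |
| 0.3 (plan) | 0.91 | 21.0 | 3.66 | 77.3% |
| 0.4 (assumed) | 0.84 | 20.2 | 3.52 | 80.5% |
| 0.5 (assumed) | 0.75 | 19.1 | 3.33 | 84.7% |

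**Step 4: what the mislabelled correlation can cost.** The worst case is a covariate with no correlation with T3: 77.3% − 73.4% = 3.9 percentage points of power.

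**Step 5: what T2 could gain.** If T2 correlates with T3 at 0.4 to 0.5, power at 164 is about 80% to 85%. If it correlates at only 0.3, power stays at 77%. The documents do not say which.

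**Step 6: sections 4.4 and 8.2 side by side.** Section 4.4 counts on an ANCOVA with a baseline value. Section 8.2 describes a model over time in which T1 and T2 are two of four responses, with adjustment dependent on observed imbalance. A mixed model with a suitable covariance structure and the pre-allocation means constrained to be equal could recover similar precision, but section 8.2 specifies neither. As written, the gain claimed in section 4.4 is not secured.

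**The case against.** **T1 is a legitimate baseline.** It is measured before randomisation, and adjusting for it is valid. Preferring T2 is an efficiency choice. This stands, and the point is limited to precision.

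**The T2 label is probably a slip.** Section 4.4 calls it the follow-up outcome and in the same paragraph places the outcome at cycle 3. This may well be right. The label still conflicts with the numbering in section 3 and needs correcting.

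**T2 is not unused.** It enters the mixed model as a response. True, but section 8.2 gives it no baseline role.

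**Figure 1 may show the order of T2 and allocation.** The figure was not available to this review. The order is unstated only in the readable text, and if the figure gives it, one sentence suffices.

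A reader might infer two stronger claims that the documents do not support:

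- *Power drops to 74% now and would rise to 85% or more with T2.* The 74% takes 0.3 as T1 with T2 and lets it decay per cycle, so T1 with T3 is 0.3² = 0.09. T2 and T3 are also one cycle apart, so the same model gives T2 with T3 as 0.3 and power of 77%. The 85% needs a different correlation model, and the two figures cannot be set against each other.
- *The primary result is biased.* If knowing the allocation shifted T2 by 2 to 5 points (an assumption), adjusting for T2 at ρ = 0.5 would move the T3 difference by ρ × shift, or 1 to 2.5 points. Nothing in the plan adjusts for T2. This is a hazard of adopting T2 without fixing its timing, and so a reason to fix the timing first.

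**Conclusion.** The point holds as one of precision and of a mislabelled input. The named baseline is a full cycle before the meals, a measurement closer to the intervention is already collected but has no baseline role, and the analysis section does not commit to the adjustment that the sample size relies on. The correlation of 0.3 is attached to a time point that is not the primary one.

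The size is modest. The label costs at most about 4 points of power, and nothing if 0.3 was meant for T3. Moving to T2 leaves power at about 77% if its correlation with T3 is 0.3, and raises it to about 80% at 0.4 or 85% at 0.5. These figures rest on SD 22, a difference of 10, 20% loss from 164, and assumed correlations above 0.3.

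The gap between 77% and the planned 80% should not be charged to the baseline choice. It is already there at ρ = 0.3 and comes mainly from the dropout step: 152 / 0.8 = 190 where the plan has 180, and 190 × 0.91 = 172.9, or 173, where the plan has 164. That is a separate matter.

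**What to change.** 1. **Sections 3 and 6.3:** state that the T2 QLQ-C30 is completed before the allocation is disclosed to the patient.
2. **Section 8.2:** pre-specify T2, together with T1, as baseline covariates for the T3 comparison, whatever the observed imbalance, and keep only T3 and T4 as responses. This avoids T2 being both covariate and outcome.
3. **Fallback:** if T2 cannot precede disclosure, use T1 as the covariate and say so.
4. **Section 4.4:** state ρ as the correlation of the chosen covariate with T3, give its source, and show power at 164 over a range such as 0.3 to 0.5, marking assumed values.

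**Cost.** No extra measurement is needed, but this is more than a wording change. T2 is measured at a home visit, randomisation is run at the hospital department, and the individual intake must follow allocation and precede the meals. The questionnaire therefore has to be scheduled ahead of disclosure and intake within the time available before cycle 2.
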